1 PROTOCOL SYNOPSIS

Financial Disclosure for US FDA Submission Required?	Q [] Yes E [] No
Test Article/ Product:	
Cataract Refractive Suite (CRS) composed of the following:
 
 1. Verion Image Guided System 2. LenSx Femtosecond laser 3. Optiwave Refractive Analysis (ORA) with VerifEye+ (with or without the VerifEye Lynk)
Objectives:	
Effectiveness Objectives
 
Primary:
 
 • To compare the refractive predictability (prediction error) between the CRS and standard manual technique at 1 month postoperative. 
Secondary:
 
 • To compare the amount of cumulative dissipated energy (CDE) expended in the eye between the CRS and standard manual technique. • To assess the average estimated aspiration fluid used during surgery between the CRS and standard manual technique. • To assess the average aspiration time spent during surgery between the CRS and standard manual technique. 

Clinical Study Design:	This is a prospective, multi-center, observer masked, randomized, active control (standard manual technique), contralateral design study.	
No. of Subjects:	This study will enroll approximately 350 subjects to initially randomize and treat 300 subjects (that could potentially increase to approximately 580 subjects enrolled and 500 subjects randomized). An interim analysis will be performed once 200 subjects have been randomized, treated and completed 1-month follow-up visits. An additional 200 subjects may be randomized and treated beyond the initially planned 300 subjects. It is planned that the study will randomize and treat between 300 and 500 subjects.	
Regions:	US and EU	
Clinical Study Duration:	
Total expected duration of the clinical investigation:
 
a) Total expected duration of the clinical investigation- up to 11 months
 
b) Expected duration of each subject's participation – up to 154 days
 
c) Planned follow-up duration – 3.5 months
 
d) Estimated time needed to select the number of subjects (enrollment period) - 6 months
	
Clinical Study Population:	Adult subjects with bilateral cataracts who are candidates to receive ReSTOR +2.5 D multifocal IOL	
Treatments:	Test Article:	The CRS is composed of the following: 
 1. Verion Image Guided System 2. LenSx Femtosecond laser 3. ORA with VerifEye+ (with or without the VerifEye Lynk)
	Administration:	Intervention during preoperative planning and during cataract surgery.
	General Description:	The CRS is composed of a series of devices that address the pre-planning stages of IOL calculation and integrates this information into the operative stage up to postoperative follow-up.

	Control Article:	Active: Standard manual technique
	Administration:	Intervention during surgery
	General Description:	Standard phacoemulsification technique
Inclusion & Exclusion Criteria:	
Inclusion Criteria:
 
 1. Adults (≥ 22 years of age at the time of surgery), diagnosed with bilateral cataracts. 2. Planned cataract surgery and implantation of ReSTOR +2.5 D multifocal IOL in both eyes. 3. Target is emmetropia (+0.50 to -0.50). 4. Clear intraocular media other than cataract in study eye(s). 5. Willing and able to complete all required postoperative visits. 6. Able to comprehend and sign a statement of informed consent. 7. Potential postoperative visual acuity of 0.2 logarithm of the minimum angle of resolution (LogMAR) or better. 8. Preoperative keratometry reading between 40.0 D to 49.0 D in the primary meridians. 9. Preoperative axial length between 21.5 mm to 27.0 mm. 10. Preoperative/Baseline corneal with-the-rule (WTR), against-the-rule (ATR) or oblique astigmatism ≤ 1.25 D. 
Exclusion Criteria:
 
 1. Significant irregular corneal astigmatism as assessed by the index relevant to the corneal topographer and investigator judgement of the topography maps 2. History of or current severe dry eyes. 3. Tear breakup time (TBUT) < 10 secs prior to randomization. 4. Retinal/uveal pathology or concurrent ocular disease including age-related macular degeneration (AMD), choroidal neovascularization (CNV), glaucoma, diabetic retinopathy, retinitis pigmentosa, optic nerve pathology. 5. Previous intraocular or corneal refractive surgery. 6. Any inflammation or edema (swelling) of the cornea, including but not limited to the following: keratitis, keratoconjunctivitis, and keratouveitis. 7. Amblyopia. 8. Previous corneal transplant. 	

	
9. Previous retinal detachment.10. Recurrent severe anterior or posterior segment inflammation of unknown etiology.11. Pregnancy at time of Screening.12. Participation in another concurrent clinical study.13. Any other ocular condition or systemic co-morbidity that the Investigator determines would confound the results of this study or would prohibit completion of the study assessments.
Effectiveness Endpoints Variables	
Primary
 
• Percentage of eyes in which the MRSE at 1 month is ≤ 0.50 D relative to predicted MRSE. 
Secondary
 
• Cumulative dissipated energy (CDE)• Estimated aspiration fluid used• Phacoemulsification aspiration time
Safety Variables	
• Adverse events• Slit-lamp examination• Intraocular pressure (IOP)• Surgical problems• Dilated fundus examination• Device deficiencies

Planned Analyses	
The primary effectiveness objective is to demonstrate superiority of the Cataract Refractive Suite (CRS) compared to standard manual techniques with respect to refractive predictability (predictive eITor) at 1 month.
 
The null and alternative hypotheses for the primary analysis are:
 
Ho: $P_c \leq P_s$
 
H_i: $P_c > P_s$
 
where P_c and P_s are the percentage of eyes with manifest refraction spherical equivalent within 0.5 D of predicted postoperative spherical equivalent at 1 month in the CRS and standard manual technique arms respectively. The primary effectiveness analysis will be analyzed using a one-sided McNemar's test at the $\alpha=0.05$ level.

	
The secondary endpoints are:
 
 • The mean CDE expended in the eye during surgery. • The mean estimated aspiration fluid used during surgery. • The mean aspiration time spent during surgery. 
The null and alternative hypotheses are the same for all secondary analysis and can be presented as:
 
Ho: $\mu_c \leq \mu_s$
 
H_i: $\mu_c > \mu_s$
 
where μ_c denotes the mean value in the CRS group and μ_s denotes the mean value in the standard manual technique group for each of the respective secondary endpoints. The secondary hypotheses will only be tested if the primary objective is met and each of the null hypotheses will be tested using a one-sided paired t-test.
 
[REDACTED]

	
The safety outcomes will be summarized with appropriate summary statistics and also listed. The study will employ an adaptive design with potential sample size adjustment based on the proportion of discordance in the primary effectiveness outcome between the study eyes. An interim analysis to assess the need for sample size re-estimation will be performed when the first 200 subjects who are randomized, treated and completed their assessment for the primary effectiveness at Month 1.

Sample Size Justification	
Based on recent clinical experience, the rates of success for the primary endpoint are assumed to be 83% and 75% for the CRS and standard manual technique arms, respectively.
 
An estimate of the discordance in outcome between eyes is not known; however, based on the assumed rates of 83% and 75% for the primary endpoint, the rate of discordance must be between 8% and 33%. For an initial sample size calculation, the midpoint value of this range, 21%, is assumed. Based on these assumptions, 267 subjects, treated contralaterally, are required to provide 90% power to reject the null hypothesis. If the proportion of discordance is 33% and all other assumptions stay the same a sample of 433 subjects is needed to provide 90% power.
 
The two samples (267 and 433) are inflated to account for up to 10% subject drop-out in the full analysis set (FAS) so the subject range increases to 300 to 500.

---------------------------	---

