9.4.2 Potential Benefits

VERION® Image Guided System: The Verion reference unit is a preoperative measurement device that captures and utilizes a high-resolution reference image of a subject's eye. It provides preoperative surgical planning functions to assist the surgeon with planning cataract surgical procedures that takes into account variables not typically considered when doing standard IOL calculation such as rotational eye movements and surgical induced astigmatism.

The Verion reference unit also supports the export of captured images of the eye (ie, scleral vessels, undilated pupil), preoperative measurement data, and surgical plans for use with the Verion digital marker and other compatible devices. These features enable automatic positioning and centration of the capsulotomy and IOL as well as placement of corneal incisions in the right location taking into account cyclorotation of the eye which would otherwise be unidentifiable without physically marking the eye pre-op.

LenSx laser: The LenSx laser is indicated for use in subjects undergoing cataract surgery for removal of the crystalline lens. It pre-cuts the anterior capsule, lens and creates the corneal incisions for easier removal of the cataractous lens in the operating room. The LenSx femtosecond laser can create corneal incisions that are single plane or multi-plane allowing for customization of the cuts. Since the LenSx device pre-cuts the eye prior to surgery, this will require less phacoemulsification power and time to remove the cataractous lens. Reduced time in the eye has been associated with less risk for potential complications such as corneal burns and others.

With the integration of the Verion to the LenSx femtosecond laser, the pre-op data collected from the Verion reference unit is transferred to the Verion Digital Marker L allowing automatic positioning and placement of the cuts. This automatic feature can decrease any error that may come from manual transcription.

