15.4.2.2 Analysis Methods

Each of the null hypotheses will be tested using a paired *t*-test; the family-wise type-I-error of 5% will be controlled using the Hochberg testing procedure outlined in Section 15.6.

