## 1 Study Objectives and Design

[figure not shown]
This statistical analysis plan (SAP) describes the statistical analysis outlined in Section 15 of the study protocol along with any additional analyses, specifications, or deviations from the protocol planned before database lock (DBL).

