### 5.3.2 Secondary Effectiveness Endpoints

Each of the null hypotheses will be tested using a one-sided paired t-test. Multiplicity adjustment will be discussed in Section 5.4.

Descriptive statistics for continuous variables will be provided by procedure group for each of the secondary effectiveness endpoints (mean CDE expended in the eye during surgery, mean estimated aspiration fluid used during surgery, mean aspiration time spent during surgery).

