## 5.4 Multiplicity Strategy

In order to control the overall type I error rate over the family of primary and secondary hypotheses, the secondary effectiveness hypotheses will only be tested if the primary effectiveness null hypothesis is rejected at the one-sided 5% significance level ( $\alpha=0.05$ ).

If the null hypothesis of the primary effectiveness endpoint is rejected, then the three secondary effectiveness endpoints will be tested using the Hochberg testing procedure. Let:

- $H_{0i}$  refers to the corresponding null hypotheses ( $i=1, 2, 3$ )

- $p_i$  refers to the p-values for  $H_{0i}$ , which will be calculated without any multiplicity adjustment. The p-values will be sorted in order of magnitude such that  $p_1 \leq p_2 \leq p_3$
- Hochberg's step-up method will proceed as follows:
  - Step 1: If  $p_3 < \alpha$  (where  $\alpha$  is 0.05, 1-sided), reject all  $H_{0i}$  ( $i=1,2,3$ ) and stop; otherwise go to Step 2.
  - Step 2: If  $p_2 < \alpha/2$  (where  $\alpha$  is 0.05, 1-sided), reject  $H_{01}$  and  $H_{02}$  and stop; otherwise go to Step 3.
  - Step 3: If  $p_1 < \alpha/3$  (where  $\alpha$  is 0.05, 1-sided), reject  $H_{01}$  and stop.

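### The protocol synopsis states the one-sided secondary hypotheses in the opposite direction to protocol Section 15.4.2.1 and SAP Section 5.2.2

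*Protocol*

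**What the plan says.** The secondary hypotheses appear in three places. Each introduces them with the same sentence, "The null and alternative hypotheses are the same for all secondary analysis and can be presented as", and each defines c as CRS and s as the standard manual technique. The synopsis, for example, says that the second mean "denotes the mean value in the standard manual technique group for each of the respective secondary endpoints".

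| Place | Null | Alternative | Test named |
|---|---|---|---|
| Protocol Section 1, synopsis, Planned Analyses | μc ≤ μs | μc > μs | one-sided paired t-test |
| Protocol 15.4.2.1 and 15.4.2.2 | μc ≥ μs | μc < μs | paired t-test, sidedness not stated |
| SAP 5.2.2 and 5.3.2 | μc ≥ μs | μc < μs | one-sided paired t-test |

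The synopsis runs the secondary tests only "if the primary objective is met and each of the null hypotheses will be tested using a one-sided paired t-test". Protocol 15.4.2.2 adds that "the family-wise type-I-error of 5% will be controlled using the Hochberg testing procedure outlined in Section 15.6". SAP 5.3.2 says "Each of the null hypotheses will be tested using a one-sided paired t-test", and SAP 5.4 says that, once the primary null is rejected, "the three secondary effectiveness endpoints will be tested using the Hochberg testing procedure", with one-sided steps of 0.05, 0.05/2 and 0.05/3.

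On the expected direction, protocol 9.4.2 says of the laser that "this will require less phacoemulsification power and time to remove the cataractous lens".

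**The concern.** In a one-sided test the direction of the alternative is the decision rule. The synopsis gives one rule for all three secondary endpoints, while Section 15 and the SAP give the opposite rule. These are the endpoints tested with family-wise error control after the primary, so they carry claims.

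If the synopsis were followed, a CRS arm that used less energy, fluid or time could not succeed, and one that used more could. Anyone who takes the success rule from the synopsis, such as an ethics committee, a reader of a registry summary or the author of a report shell, would have it backwards.

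**Working it through.** **1. Are the labels swapped?** No. All three places define c as CRS and s as standard manual, and all three apply one pair of hypotheses to the same three endpoints. The reversal lies in the inequality signs alone.

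**2. Which statement is the odd one out?** Section 15.4.2.1 and SAP 5.2.2 agree. The SAP says that it "describes the statistical analysis outlined in Section 15 of the study protocol", and it notes no departure on direction. Protocol 9.4.2 expects less phaco power and time with the laser, which fits μc < μs for CDE and aspiration time. It does not mention fluid, so the direction for fluid rests on Section 15.4.2.1 and SAP 5.2.2. The synopsis signs are the same as those of the primary hypotheses printed shortly before them, where a higher value is better. A carry-over is plausible, but the documents do not state the cause.

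**3. Does the amendment log explain it?** No. Amendment 1 lists statistical changes to Sections 1 and 15, but neither amendment lists a change of direction for the secondary hypotheses.

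**4. Sample sizes for the degrees of freedom.** The plan's own figures come from the primary endpoint (protocol 15.10, SAP 7): d = 0.83 − 0.75 = 0.08, one-sided α = 0.05, 90% power, discordance ψ = 0.21 or 0.33, Miettinen approximation:

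n = [z₀.₉₅·ψ + z₀.₉₀·√(ψ² − d²(3 + ψ)/4)]² / (ψ·d²)

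- ψ = 0.21: n = 266.4, rounded up to 267. This matches the plan.
- ψ = 0.33: n = 432.05, rounded up to 433. This matches the plan.

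These figures only supply n. The contradiction does not depend on them.

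**5. What the reversal does to the test.** Let D = CRS minus manual within a subject, and let t be the paired t statistic with n − 1 df.

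- Section 15.4.2.1 and SAP: p = P(T ≤ t), reject for large negative t.
- Synopsis: p = P(T ≥ t), reject for large positive t.
- So p(synopsis) = 1 − p(Section 15.4.2.1) for any data. No effect size or SD is needed.

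The 5% critical values of |t| are 1.6506 (n = 267), 1.6500 (n = 300), 1.6484 (n = 433) and 1.6479 (n = 500). The two rejection regions, about t < −1.65 and t > +1.65, do not overlap.

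Results lying exactly on the Hochberg steps:

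| p under Section 15.4.2.1 and SAP | p under synopsis |
|---|---|
| 0.05 | 0.95 |
| 0.025 | 0.975 |
| 0.0167 | 0.983 |

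One example: t = −2.0 on 266 df gives p = 0.023 under Section 15.4.2.1 and p = 0.977 under the synopsis.

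**6. Illustration under assumed effects.** The documents give no effect or SD for the secondary endpoints, so the reductions below are assumptions, in units of the SD of the paired difference. The entries are probabilities of rejection for one endpoint at one-sided 5%, from the noncentral t distribution.

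| Assumed reduction with CRS | n = 267, Section 15 and SAP | n = 267, synopsis | n = 433, Section 15 and SAP | n = 433, synopsis |
|---|---|---|---|---|
| 0.1 SD | 0.494 | 0.0005 | 0.667 | 0.0001 |
| 0.2 SD | 0.947 | <0.0001 | 0.994 | <0.0001 |
| 0.3 SD | 0.999 | <0.0001 | >0.999 | <0.0001 |

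**The case against.** The strongest reply is that nothing will go wrong in practice. The synopsis gives no alpha for the secondary tests and does not mention Hochberg, so nobody can run the analysis from it alone. Anyone who turns to Section 15 or the SAP finds one consistent direction. On this view the p and 1 − p figures merely restate that the signs are opposite, and the power table describes a test that no analysis section specifies. That is right as far as it goes: it limits the point to a consistency correction, and no bias in the results is claimed. It does not remove the contradiction, because the synopsis is current protocol text and states the direction of a one-sided test.

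The second reply is that the signs may be a misreading of the PDF. The synopsis text has visible misreads, and inequality signs have dropped out elsewhere (the primary endpoint in 8.4.1, the age limit in Section 10). This is possible. However, those are lost signs. Here two different symbols on two lines would have had to flip into a coherent pair, which is less likely. The source PDF settles it.

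The third reply is that adding the word one-sided to 15.4.2.2 resolves nothing, since 15.4.2.1 is already directional. That is fair, and the addition is optional.

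Finally, protocol Section 5 requires a written amendment for any modification, with ethics approval before implementation unless the change is only logistical or administrative. That belongs in the cost.

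**Conclusion.** The concern holds. As extracted, the synopsis prints both secondary hypothesis lines the wrong way round relative to Section 15.4.2.1 and SAP 5.2.2, for all three secondary endpoints, and nothing in the documents explains it. The size is exact: the p-values are complementary and the 5% rejection regions are disjoint.

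The consequence is limited. Section 15 and the SAP give one coherent rule, so the analysis as programmed is probably right. The primary endpoint, sample size, interim analysis and alpha do not change. It should still be fixed, because a decision rule in current protocol text is wrong as written. The conclusion assumes that the two symbols in the source PDF read as extracted.

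**What to change.** Check the two synopsis lines against the source PDF. If they read as extracted, change the null to μc ≥ μs and the alternative to μc < μs, matching Section 15.4.2.1 and SAP 5.2.2. Do this before the secondary endpoints are compared by procedure group. As an optional tidy-up in the same edit, call the paired t-test in 15.4.2.2 one-sided, as SAP 5.3.2 does.

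The text change is two lines, plus one word if the option is taken. It has no cost in data, sample size or programming. The administrative cost is whatever Section 5 of the protocol requires: an amendment, with or without prior ethics approval depending on whether the sponsor classes the correction as administrative. It can be carried with the next amendment if that falls before the comparison.

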15.10 Sample Size Justification

The rates of success for the primary endpoint are assumed to be 83% and 75% for the CRS and standard manual technique arms respectively. These assumptions are based on data from the AnalyzOR Retrospective Data Exploration Study (Data on File).

An estimate of the discordance in outcome between eyes is not known; however it's estimated that discordance will be in the range 8% to 33%. For an initial sample size calculation, the midpoint value of this range, 21%, will be assumed. Based on these assumptions 267 subjects, treated contralaterally, are required to provide 90% power to reject the null hypothesis for a one sided McNemars test at the 5% level using the approximation from Miettinen (Miettinen 1968). If the proportion of discordance is 33% and all other assumptions stay the same a sample of 433 subjects is needed.

The initially planned sample size of 267 is inflated to allow for up to 10% drop out; this inflation yields a sample size of 300 subjects. Inflation of the sample size of 433 to allow for up to 10 % drop out yields a sample size of 485; the sample size of 500 is selected so that the maximum sample size will be divisible by the block size of 50.

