## **7 Sample Size and Power Calculations**

The rates of success for the primary endpoint are assumed to be 83% and 75% for the CRS and standard manual technique arms respectively. These assumptions are based on data from the AnalyzOR Retrospective Data Exploration Study (Data on File)..

An estimate of the discordance in outcome between eyes is in the range 8% to 33%. For an initial sample size calculation, the midpoint value of this range, 21%, will be assumed. Based on these assumptions 267 subjects, treated contralaterally, are required to provide 90% power to reject the null hypothesis for a one sided McNemars test at the 5% level using the approximation from Miettinen (Miettinen 1968). If the proportion of discordance is 33% and all other assumptions stay the same a sample of 433 subjects are needed.

The initially planned sample size of 267 is inflated to allow for up to 10% drop out; this inflation yields a sample size of 300 subjects. Inflation of the sample size of 433 to allow for up to 10 % drop out yields a sample size of 485; the sample size of 500 is selected so that the maximum sample size will be divisible by the block size of 50.

The study will also employ an adaptive design with potential sample size adjustment based on the proportion of discordance from the interim analysis. This study will enroll approximately 350 subjects to initially randomize and treat 300 subjects (that could potentially increase to approximately 580 subjects enrolled and 500 subjects randomized). Based on the calculation from the interim analysis an additional 200 subjects may be randomized and treated thus the study will randomize and treat a total sample size in the range of 300 to 500 subjects. Any additional sample size will be added in blocks of 50 in order to prevent any back-calculation of the interim study results.

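### Do the assumed 83% and 75% success rates really cap between-eye discordance at 33%, and does the sample size suffer if they do not?

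*Protocol*

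**What the plan says.** The synopsis takes as its starting point that "the rates of success for the primary endpoint are assumed to be 83% and 75% for the CRS and standard manual technique arms, respectively". It says that the discordance between eyes is not known, then that "based on the assumed rates of 83% and 75% for the primary endpoint, the rate of discordance must be between 8% and 33" per cent. From there "the midpoint value of this range, 21%, is assumed", and "267 subjects, treated contralaterally, are required to provide 90% power to reject the null hypothesis". For the upper case it says: "If the proportion of discordance is 33% and all other assumptions stay the same a sample of 433 subjects is needed".

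The detailed sections use the same range in softer terms. Protocol 15.10 says "it's estimated that discordance will be in the range 8% to 33" per cent. SAP 7 says "An estimate of the discordance in outcome between eyes is in the range 8% to 33" per cent. Protocol 15.10 and SAP 7 also name the method: "a one sided McNemars test at the 5% level using the approximation from Miettinen". They add 10% for drop-out, which gives 300 subjects initially, and 485 rounded up to a maximum of 500 in blocks of 50.

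None of the three places says how 33% was obtained or mentions correlation between fellow eyes.

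**The concern.** In a contralateral design the two success rates fix only the margins of the paired two-by-two table. They set a lower and an upper limit on discordance, and the upper limit is 42%, not 33%. The synopsis therefore presents as a mathematical consequence something that needs another assumption.

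This looks important because the whole size of the trial hangs on the range. Its midpoint gives the 21% planning value and 267 pairs. Its top end gives 433 pairs and hence the maximum of 500. A reader who takes the synopsis literally would believe that 433 pairs cover the worst case the assumed rates allow. They do not: at 42% the same formula asks for 555 pairs, more than the maximum the plan permits.

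**Working it through.** **Inputs.** Success rates: CRS *pc* = 0.83, manual *ps* = 0.75, so *d* = 0.08 (synopsis; Protocol 15.10; SAP 7). One-sided 5% McNemar test, 90% power, Miettinen approximation (Protocol 15.10; SAP 7). Drop-out 10%.

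**Step 1: reproduce the plan's figures.** With discordance ψ, z_a = 1.645 and z_b = 1.2816,

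n = [z_a·ψ + z_b·√(ψ² − d²(3+ψ)/4)]² / (ψ·d²)

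- ψ = 0.21: [0.3454 + 1.2816 × √(0.0441 − 0.005136)]² / 0.001344 = 266.4, so 267. Matches.
- ψ = 0.33: [0.5428 + 1.2816 × √(0.1089 − 0.005328)]² / 0.002112 = 432.0, so 433. Matches.

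**Step 2: what the rates alone allow.**

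- Minimum: 0.83 − 0.75 = 0.08, as stated.
- Maximum: (1 − 0.75) + (1 − 0.83) = 0.25 + 0.17 = 0.42. The table that attains it is valid: both succeed 58%, CRS only 25%, manual only 17%, both fail 0%.
- Independent eyes: 0.83 × 0.25 + 0.75 × 0.17 = 0.2075 + 0.1275 = 0.335.

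The stated 33% is therefore consistent with independence as the upper limit. That is a reconstruction, since the documents give no derivation.

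**Step 3: the correlation each value implies.** The probability that both eyes succeed is (1.58 − ψ)/2, so

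φ = [(1.58 − ψ)/2 − 0.6225] / √(0.83 × 0.17 × 0.75 × 0.25), with denominator 0.1627

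| ψ | φ |
|---|---|
| 0.21 | +0.38 |
| 0.33 | +0.015 |
| 0.335 | 0 |
| 0.42 | −0.26 |

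Reaching 42% requires clearly negative correlation, with no subject failing in both eyes. Protocol 9.2 lists keratometry, IOL calculation, surgeon factors, astigmatism and IOL type as drivers of refractive accuracy. Several of these are common to both eyes of a subject: both eyes receive the same IOL model, and the same planner is used for both (Table 6-1 footnote). Shared causes push φ up, not down.

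**Step 4: does any planned number move under non-negative correlation?** The limit is then 33.5% rather than 33%.

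- n at 0.335 = 438.9, so 439 pairs.
- 439 / 0.9 = 487.8, so 488 subjects. In blocks of 50 this is 500, as planned.
- Midpoint: (8 + 33.5)/2 = 20.75, which still rounds to 21%.
- 500 subjects less 10% leaves 450 pairs. Their fixed-sample power at 33.5% is 90.6%, and they hold 90% up to about 34.3% discordance, where φ = (0.6185 − 0.6225)/0.1627 ≈ −0.02.

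Nothing moves: 21%, 267, 300 and 500 stand, and 433 remains correct for the 33% it is tied to.

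**The case for a change.** The strongest opposing case is that a planning input which fixes both the starting size and the ceiling should carry its true justification. The synopsis and the body give different grounds for the range, and neither gives the real one. Interim re-estimation is only a partial safeguard: it adjusts on observed discordance, but the increase stops at 500 and is barred if conditional power at 500 is below 50% (Protocol 15.8; SAP 5.6). If fellow-eye outcomes were strongly negatively correlated, the cap would be too low: 555 pairs at 42%, or 617 subjects after drop-out.

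What stands is that the synopsis sentence is false as written, that the premise is unstated, and that 433 pairs fall slightly short of the independence limit, by six pairs. What does not stand is any practical consequence. The 42% case rests on a correlation pattern that the design gives no reason to expect. The six-pair shortfall disappears in the rounding to 500. The synopsis also ties 433 explicitly to 33% discordance, so a reader reaches a worst-case reading only by joining that sentence to the overstated one before it.

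**Conclusion.** This is a clerical overstatement in the synopsis. The range is an estimate that assumes non-negative correlation between a subject's eyes, and Protocol 15.10 and SAP 7 already call it an estimate. Rewording the synopsis would put a sensible premise on paper but would change nothing that the trial does or concludes. The starting size, the 500 maximum and the interim rule stay as they are. The final McNemar test uses the discordance actually observed, so its validity does not depend on the planning range.

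The conclusion rests on the 83% and 75% rates being taken as given and on fellow-eye correlation that is zero or positive. At zero, the upper requirement is 439 pairs rather than 433, still inside the planned maximum. The point should not be read as a sample-size defect.
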